- f. Patients with a hypersensitivity to TXA or any of the ingredients

- g. History of venous or arterial thrombotic events because use of tranexamic acid is a risk factor for thromboembolism.
- h. Conditions that predispose patients to thromboembolic events (e.g. thrombophilias, autoimmune diseases such as lupus, active cancer, congestive heart failure) because of increased risk of thrombosis
- i. Patients taking factor IX complex concentrates or anti-inhibitor coagulant concentrates (e.g. FEIBA NF)
- j. Seizure disorder because the use of tranexamic acid has been associated with postoperative seizures
- k. Patients with a baseline creatinine 1.2 or higher, history of renal insufficiency, or renal disease because of the risk of toxicity in patients with preexisting disease.
- l. Patients with frank hematuria because ureteral obstruction due to clot formation has been reported in patients with upper urinary tract bleeding who were treated with tranexamic acid
- m. History of retinal disease as cases of central retinal artery and vein obstruction have been reported in patients treated with tranexamic acid
- n. Patients with acquired defective color vision
- o. Patients with retinal diseases; cases of central retinal artery and central retinal vein obstruction have been reported in patients treated with intravenous tranexamic acid.

Inclusion:

-Pregnant women 18-54 years old delivering at Navy Medical Center San Diego (NMCS D)

Recruitment Process:

Patients will be identified in the antenatal clinics of Naval Medical Center San Diego. All patients that meet the inclusion criteria will be offered inclusion in the study.

All English speaking women who are eligible to receive care at NMCS D and presenting to NMCS D's Labor and Delivery Unit, who are at least 18 years old, not older than 54, and who are scheduled to deliver at NMCS D, will be given verbal and/or a written information sheet about the study and a description of what the study entails. OBGYN staff providers and residents will also be given an information sheet about the study. Opportunities for potential participant recruitment include:

- NMCS D Prenatal Registration
- NMCS D Gestational Diabetes education classes
- NMCS D Labor and Delivery tour of the unit

Subject eligibility and screening will take place prior to offering potential subjects the opportunity to participate in the study. An eligibility and screening tool will be used as part of the recruitment process.

Consent Process:

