 2. For patients that present for delivery at a gestational age less than 34 weeks, it will be recommended that they discard their breast milk until 24 hours after their last TXA administration.
 3. Order TXA for patient in ESSENTRIS
 4. RN to pull TXA from Pyxis and put in patient's room
 5. TXA per protocol (see supplement A)
 6. The use of additional uterotonics or single additional dose of TXA is at the discretion of the delivering provider
 7. For patient monitoring protocol please see Supplement B.
 8. All neonates are monitored for a minimum of 24 hours either by the NICU or the Newborn Nursery. Vitals are taken every four hours. Weights and bilirubin levels are obtained daily. Daily physical exams are performed.
3. Data collection
 1. Participants will be assigned an individualized subject number upon their enrollment to the study.
 2. Participants will be followed from their enrollment into the study until six weeks postpartum.
 3. An Excel spreadsheet will be used to collect the variables as listed above.
 4. Once the variable collection is complete, the information will become de-identified.

5. Chart review will be performed to estimate institutional rates of the secondary outcomes in the 12 months preceding the initiation of the protocol.
4. Data Analysis
 1. SPSS software will be used for our statistical analysis. Normal distribution will be assumed given the intended number of patients for analysis. Categorical variables will be analyzed using the Chi-square test. The t-test will be utilized for the comparison of continuous interval data.
 2. Using a postpartum hemorrhage rate of 2.86% (institutional data), and a desired impact of reducing the hemorrhage rates by 50% after implementation of the new protocol, then 890 subjects would need to be recruited to answer the question.
 3. The secondary outcomes will also be tested against institutional rates. Institutional rates will be estimated by record sampling done at the time of data collection.

Experimental Procedures:

See supplement A

Research materials collected:

Variables to be collected:

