Age, race/ethnicity, DoD status, BMI, gestational age, # of fetuses, gravidity, parity, admission diagnoses, admission estimated fetal weight, intrapartum diagnoses, postpartum diagnoses, misoprostol use, oxytocin use, mechanical dilation, duration of labor, magnesium sulfate use, planned mode of delivery, mode of delivery, birth weight, indication for operative delivery, neonatal outcomes, maternal outcomes, admission to the intensive care unit, uterotonic use, mechanical tamponade, blood product transfusion, estimated blood loss, qualitative blood loss, cumulative blood loss, laboratory results, post-delivery laboratory results

Confounding variables:

Management of the 3rd stage of labor

Source of the data:

Outpatient records (AHLTA), Inpatient records (Essentris). As providers, the investigators have access to these systems as a standard of care for patients receiving care from investigator-providers.

Paper records created in the Labor and Delivery department during the course of a delivery.

The data collected will be measured against the historic PPH rates of NMCSO over a period of time to be determined.

Protection of Privacy:

Each participant will be given a unique study number. A master list with only the minimal Personal Identifiable Information (PII) needed for follow up and their study number will be kept in the PI's office on a CAC PIN protected computer in the PI's locked office. The master list will be used to track the results of the study participant's data collection.

An Excel spread sheet will be used to collect this information using only the participants unique study number and stored electronically on a CAC PIN protected computer in the PI's locked office.

All data and PII will be destroyed (shred or deleted) at the conclusion of this project.

Risks:

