To satisfy these two areas of responsibility, the research monitor may discuss the research protocol with the investigators, interview study subjects, and consult with others outside of the project about the research. In the event a problem is identified, they have authority to stop a research protocol in progress, remove individual subjects from a study, and take whatever steps are necessary to protect the safety and well-being of subjects until the IRB can assess the monitor's report.

Research monitors are required to promptly report their medical monitoring and oversight monitoring observations and findings to the IRB or other designated official.

Data Collection Sheets

See attached Excel spreadsheet.

Objectives:

The obstetrics literature to date focuses on TXA use prior to non-emergent cesarean delivery or in response to hemorrhage. Data is lacking in the area of prophylactic use prior to vaginal delivery. The aim of this study will be to assess the ability of TXA to prevent postpartum hemorrhage.

Primary Outcome:

To assess the efficacy of TXA in reducing the incidence of postpartum hemorrhage when given prophylactically prior to all deliveries.

The American Congress of Obstetricians and Gynecologists published 'ReVitalize' in 2014 that defined postpartum hemorrhage as blood loss of ≥ 1000 cc or blood loss accompanied by sign/symptoms of hypovolemia to include blood transfusion within 24 hours following the birth process (includes intrapartum loss).

[figure not shown]
For the purposes of this study, postpartum hemorrhage will be defined as a blood loss of ≥ 1000 cc in addition to all patients requiring blood transfusion (even if blood loss is less than 1000cc).

Secondary outcomes:

Estimated blood loss (EBL) – measured in cubic centimeters. EBL will be decided upon by the delivery provider. All delivering providers at this institution have received formal instruction on estimation of blood loss and a visual aid is available at every bedside and in the operating room (see below).

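### The historic comparator for the primary outcome is not pinned down: its period is open, and the eligibility criteria, PPH definition and blood-loss measurement rules are not applied to the historic records

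*Combined protocol and SAP*

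**What the plan says.** Research Design describes a prospective cohort with one arm. Four places bear on the control for the primary outcome.

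- Source of the data: "The data collected will be measured against the historic PPH rates of NMCSO over a period of time to be determined".
- Study Procedures, 3. Data collection, item 5: "Chart review will be performed to estimate institutional rates of the secondary outcomes in the 12 months preceding the initiation of the protocol".
- Study Procedures, 4. Data Analysis, item 3: "The secondary outcomes will also be tested against institutional rates". It continues: "Institutional rates will be estimated by record sampling done at the time of data collection".
- Study Procedures, 4. Data Analysis, item 2 (repeated in Research Design, d): a PPH rate of 2.86%, described only as institutional data, and a hoped-for halving give 890 subjects.

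For the test, Data Analysis item 1 says "Categorical variables will be analyzed using the Chi-square test", without saying whether that is one-sample or two-sample. For participants, Recruitment Process says "Subject eligibility and screening will take place prior to offering potential subjects the opportunity to participate in the study". The Primary Outcome section defines PPH for this study as blood loss of at least 1000 cc, or any transfusion. Under Secondary outcomes, blood loss is estimated by eye (EBL), weighed once it reaches 500 cc (QBL), and summed when bleeding continues later (CBL).

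**The concern.** With no concurrent control, the primary result is a comparison of 890 treated women with whatever the historic rate turns out to be. Three things about that rate are open.

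**Period and timing.** The period is not set, and no section says who sets it or when. Data Analysis item 3 places record sampling at the time of data collection, and the Safety Analysis Plan says participant data are collected in real time. The reference could thus be settled while outcomes are visible.

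**Which rate is tested.** The word *also* in Data Analysis item 3 implies that the primary outcome is tested against an institutional rate. The plan does not say whether this is the 2.86% or a new estimate. The 2.86% comes without dates, denominator, population or PPH definition. The record sample has no stated size.

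**Comparability.** Participants are screened against fifteen exclusions (a to o), have PPH defined one way, and have blood loss measured under a stated rule. None of this is required of the historic records.

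At stake is attribution: a gap between participants and records on any of these could be read as an effect of tranexamic acid, or could mask one.

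**Working it through.** **Inputs from the plan:** n = 890; p0 = 2.86%; halving, so p1 = 1.43%. **Assumed, because not stated:** two-sided 5% level (2.5% in the benefit tail), 80% power, the size of any mismatch, and the number of historic records m.

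**1. The plan's figure.** One-sample test against a known rate:

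N = [(1.960·√(p0(1−p0)) + 0.8416·√(p1(1−p1))) / (p0 − p1)]²
= [(1.960 × 0.16668 + 0.8416 × 0.11872) / 0.0143]² = 889.99, i.e. 890.

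Other settings come close: one-sample, one-sided 5%, 90% power gives 888.8; two-sample, one-sided 5%, 80% power, three historic records per treated woman gives 884.5. So 890 is consistent with a known reference but does not prove that one is meant.

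**2. Effect of a wrong reference.** Benefit is declared at or below k, the largest count with P(X ≤ k | 890, reference) ≤ 0.025. False benefit is P(X ≤ k | 890, 2.86%). Power is P(X ≤ k | 890, 1.43%). A reference that is too high threatens the first; one that is too low threatens the second.

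| Reference used | k | False benefit | Power for a true halving |
|---|---|---|---|
| 2.288% (20% too low) | 11 | – | 38% |
| 2.574% (10% too low) | 13 | – | 60% |
| 2.86% (correct) | 15 | 1.7% | 79% |
| 3.146% (10% too high) | 17 | 4.9% | – |
| 3.432% (20% too high) | 19 | 11.2% | – |

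The false-benefit column should be read against 2.5%, not 5%.

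**3. A sampled rate treated as known, with no mismatch.** For each possible historic count h out of m, set r = h/m and let k(r) be the largest count with (r − k/890)/√(r(1−r)/890) ≥ 1.96. Sum P(h)·P(X ≤ k(r) | 890, 2.86%) over h. False benefit is 6.4% for m = 890, 3.9% for 2,000 and 3.2% for 3,000. A two-sample Chi-square, enumerated in the same way, gives 2.5%, 2.2% and 2.1%.

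**4. Power of the two-sample test with 890 treated.** Power = Φ[(p0 − p1 − 1.96·s0)/s1], where s0 = √(p̄(1−p̄)(1/890 + 1/m)), s1 = √(p0(1−p0)/m + p1(1−p1)/890), and p̄ is the pooled rate. For m = 890: p̄ = 2.145%, s0 = 0.006868, s1 = 0.006860, so Φ(0.122) = 55%. For m = 2,000, 3,000 and 4,000 the power is 65%, 69% and 72%.

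**5. Events expected.** 890 × 1.43% = 12.7 to 890 × 2.86% = 25.5. Shifts of one to four events in the threshold therefore matter.

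**The case against.** The plan is not empty here. The 12-month review covers secondary outcomes that include blood loss and transfusion, which are the components of the study's PPH definition. The second sentence of Data Analysis item 3 is not confined to secondary outcomes. A reader might infer from the open period that no usable comparator is planned at all; the documents do not support that. One review could serve both sets of outcomes. It remains true that no section says it does.

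The mismatch sizes are assumed. Most exclusions concern thrombotic, renal, retinal, seizure or hypersensitivity risk, and most of the listed high-risk factors for hemorrhage are not excluded. The documents do not show that applying the criteria would move the historic rate much. A reader might infer that the comparison is tilted toward the drug; nothing in the documents gives a direction.

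A reader might also infer that freedom to choose the window alone produces a large false-positive rate. It does not if the true rate is constant: at an assumed 3,000 deliveries a year, simulation with the Chi-square test gives a false benefit of 2.1% for a fixed 12 months and 3.0% for the best of 12, 24 or 36 months. The exposure comes from real differences between periods or populations.

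Finally, restricting records by eligibility does not remove selection by consent, and using the study definition does not ensure that past blood loss was measured in the same way. Both points stand, and they limit what the fix can achieve.

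**Conclusion.** The concern holds as an omission that affects the primary comparison. The period, record set, eligibility rule, PPH definition, measurement method and test value of the only control are unspecified, and the plan's wording lets the reference be chosen while outcomes accrue. It should be settled before the primary analysis can be interpreted.

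The size is conditional. At 890 women and an assumed two-sided 5% level, relative reference errors of 10% to 20% move false benefit to between 4.9% and 11% (nominal 2.5%, actual 1.7%), or power to between 60% and 38% (from 79%). Treating a sampled rate as known gives a false benefit of 3.2% to 6.4% for 3,000 down to 890 records. These illustrate sensitivity and do not estimate bias in this study.

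Nor does this show that 890 is wrong or that more women must be enrolled. The figure reproduces for a fixed, known rate under assumed error levels. What is missing is a statement of whether the reference is fixed or estimated.

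**What to change.** 1. In Data collection, item 5, extend the 12-month chart review from secondary outcomes to primary and secondary outcomes.
2. Replace the sentence under Source of the data with, for example: *The comparator is all deliveries in the 12 months before the protocol starts that satisfy the inclusion and exclusion criteria as far as records show, with PPH derived by the study definition. The period, record set and number of records are fixed before the first participant is enrolled or, if enrolment has begun, before anyone involved in the choice has seen participant outcomes.* Fixing them only before analysis would not be enough, because outcomes are collected in real time.
3. Change Data Analysis, item 3, to match. For historic deliveries, record how blood loss was measured (EBL, QBL or CBL), mode of delivery and hemorrhage risk category. Report any change in measurement practice as a limitation.
4. State the test. If the rate is re-estimated, use the two-sample Chi-square and restate the power (about 55%, 65%, 69% or 72% with 890, 2,000, 3,000 or 4,000 records); larger enrolment is not required for this correction. If 2.86% is kept as a fixed value, use a one-sample test and give that rate's dates, denominator, eligibility rule and PPH definition in place of the text in step 2.
5. Give a stratified or standardised comparison as supporting only, since about 13 to 25 events are expected.

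**Cost:** wording and some extra abstraction. Deriving historic PPH adds little, because the planned review already covers its components. Some exclusions will be poorly recorded in old charts, the stated power falls if the rate is re-estimated, and selection by consent remains a limitation.

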9. WHO Recommendations for the Prevention and Treatment of Postpartum Haemorrhage. Geneva: World Health Organization; 2012.
10. WOMAN Trial Collaborators. Effect of early tranexamic acid administration on mortality, hysterectomy, and other morbidities in women with post-partum haemorrhage (WOMAN): an international, randomised, double-blind, placebo-controlled trial. Lancet. 2017 Apr 26.

Research Design:

a. General Approach: Prospective Cohort study

b. Description: Phase 4

c. Methods: One Arm

d. Statistical Analysis:

- SPSS software will be used for our statistical analysis. Normal distribution will be assumed given the intended number of patients for analysis. Categorical variables will be analyzed using the Chi-square test. The t-test will be utilized for the comparison of continuous interval data.

-Using postpartum hemorrhage rate of 2.86% (institutional data), and a desired impact of reducing the hemorrhage rates by 50% after implementation of the new protocol, then 890 subjects would need to be recruited to answer the question.

e. Safety Analysis Plan:

- Data collection for each participant will occur in real time during pre and post delivery times, therefore safety monitoring of the patient and data will be simultaneous.
- A Research monitor has been appointed to oversee the safe and ethical conduct of the study. Additionally, the Research Monitor will provide review and comment on any adverse events. The Research Monitor is not a member of the investigative team. The role of the Research Monitor is as follows:
 1. monitor the consent process to ensure an absence of coercion
 2. monitor data collection/clinical outcome
 3. review all adverse event reports with comments from the PI and forward to the IRB with his/her own comments. Adverse events must be received by the IRB within 5 business days of occurrence or reporting (within 24 hours for serious adverse events)
 4. ensure the inclusion/exclusion criteria are followed
 5. review data security measures
- Any emerging safety concerns to include any adverse event rate higher than this institution's historical average will result in a halt to the study.

Subject Population:

Pregnant women presenting for delivery at NMCSO

a. Exclusion/Inclusion criteria:

Exclusion:

- a. Age less than 18 years
- b. Planned cesarean hysterectomy
- c. Current anticoagulant use
- d. Subarachnoid hemorrhage
- e. Any active/current intravascular clotting (i.e. venous thromboembolic events)

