Appendix L

Examples of Estimating Blood Loss

Zuckerwise. Estimated Obstetric Blood Loss With Visual Aid. *Obstet Gynecol* 2014.

Delivering providers will also adhere to NAVMEDWESTINST 6320.20, which specifies that once an EBL reaches 500cc, the delivering provider will move from an *estimation* of blood loss to utilizing a *quantitative* blood loss (QBL). QBLs are obtained by the weighing of chux pads, drapes, and linens that have been soiled (after first calibrating the scale to remove the original weight of the contaminated product). It also includes the blood that has been collected in the suction canister in the operating room.

In instances when EBL is decided upon at delivery, and ongoing bleeding occurs after the provider has left the room (and is called back), a QBL should be obtained. The QBL should be added to the initial EBL for a *cumulative* blood loss (CBL).

Percent decrease in hematocrit (Hct) – The percent change of the patients' Hct obtained on admission from that obtained after delivery. A post-operative Hct is routinely obtained six hours following a cesarean delivery. A Hct is not routinely obtained for patients having a vaginal delivery unless EBL exceeds 500cc. A post vaginal delivery Hct will not be obtained in patients for the sole purpose of this research study.

Rates of blood transfusion – The number of patients requiring blood transfusion divided by the total number of deliveries.

The types and amounts of products transfused – in patients requiring transfusion, the type of product (i.e, packed red blood cells, whole blood, fresh frozen plasma, platelets, and cryoprecipitate) will be recorded, along with how many of each type they received.

The use of uterotonic agents – in patients requiring uterotonic agents beyond the first bolus of oxytocin (i.e. second bolus of oxytocin, methylergonovine, 15-methyl Prostaglandin F_{2α}, misoprostol) will be recorded, along with how many doses of each

The need for surgical intervention – the number of patient's that require surgical intervention following a vaginal delivery for the purposes of controlling excessive blood loss divided by the total number of vaginal deliveries

The need for reoperation - the number of patients that require return to the operating room following a cesarean delivery for the purposes of controlling excessive blood loss divided by the total number of cesarean deliveries

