Rates of hysterectomy – the number of patients requiring hysterectomy divided by the total number of deliveries

Admission to the Intensive Care Unit (ICU) - the number of patients requiring admission to the intensive care unit secondary to excessive blood loss divided by the total number of deliveries

Neonatal outcomes – incidence of fetal anemia, infection, hyperbilirubinemia, neurologic outcomes, and neonatal intensive unit admissions

Maternal mortality – incidence of mortality

Additionally, postpartum hemorrhage risk assessment will be utilized to stratify patients with regard to primary and secondary outcomes.

- Patients will be risk stratified to one of three risk categories depending on admission and intrapartum risk factors
 - High Risk Factors:
 - Placenta previa/ low lying placenta
 - Suspected accreta or percreta
 - Platelet count <70,000
 - Active bleeding
 - Known coagulopathy
 - Two or more medium risk factors
 - Medium Risk Factors:
 - Prior cesarean delivery, uterine surgery, or multiple laparotomies
 - Multiple gestation
 - > 4 prior births
 - Prior obstetric hemorrhage
 - Large myomas
 - EFW >4000
 - BMI > 40
 - Hct < 30%
 - Chorioamnionitis
 - >24 hours on Oxytocin
 - Magnesium sulfate
 - Low Risk: all patients not falling in the medium or high risk categories

Importance to Navy Medicine:

Beyond the potential impact that this study has in the reduction of maternal morbidity and mortality, it can also allow for perspective into resource management. Some of the Navy Military Treatment Facilities (MTFs) have limited blood bank stock, and massive hemorrhages requiring ongoing transfusion of products can quickly deplete the entirety of the supply. If we can find a solution that will reduce the number of instances where transfusion is necessary we can help to preserve limited resources. Likewise, this preventive measure will also have the potential to (cost) reduce the need for additional uterotonics, personnel, supplies and ICU beds.

There will be no collaboration with outside institutions.

Supplement A: TXA Protocol Administration (Modified from the NMCS Maternal Child Executive Committee's Policy)

1. TXA comes in a 1000 mg/10 mL vial. Nursing staff will pull this from the Pyxis at the same time they bring Oxytocin into the L&D room.
2. Add 1000 mg (or 1 vial) of 1000 mg/10 mL to 100 mL normal saline (100 mg/mL)
 - a. Bolus: 1 gram IV over 10 minutes
 - i. Set infusion pump rate to 600 mL/hr

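### The study's own hemorrhage definition has no time window and no bleeding indication for transfusion, and the 2.86% historic rate it is compared with has no stated definition, so the two rates may not count the same events

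*Combined protocol and SAP*

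**What the plan says.** Under Objectives, Primary Outcome, the protocol first cites the 2014 ReVitalize definition. This is a loss of at least 1000 cc, or "blood loss accompanied by sign/symptoms of hypovolemia to include blood transfusion within 24 hours following the birth process (includes intrapartum loss". It then sets its own rule for the study: "postpartum hemorrhage will be defined as a blood loss of ≥ 1000 cc in addition to all patients requiring blood transfusion", including women who lost less than 1000 cc. That sentence contains no time limit and no reason for the transfusion.

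Under Study Procedures, Data collection: "Participants will be followed from their enrollment into the study until six weeks postpartum".

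The secondary transfusion outcome is equally open: "The number of patients requiring blood transfusion divided by the total number of deliveries". Neighbouring secondary outcomes do state a cause. ICU admission is "the number of patients requiring admission to the intensive care unit secondary to excessive blood loss divided by the total number of deliveries", and surgical intervention and reoperation are likewise limited to control of excessive bleeding.

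The design is one arm. The comparator enters the sample-size statement as "Using postpartum hemorrhage rate of 2.86% (institutional data", with no definition or window. The section on the source of the data leaves the historic period to be determined. The 12-month chart review is specified for the secondary outcomes only.

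**The concern.** The study wrote a new rule directly after the cited one and changed its content, so a reader cannot tell which parts of the cited definition carry over. Taken as written, a transfusion at three weeks, or one given for a reason other than delivery bleeding, makes a woman a primary event even if she lost less than 1000 cc.

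With no concurrent control, any difference in how events are counted in the two periods goes straight into the estimated effect. If the 2.86% reflects 24 hours or the delivery stay while study women are searched for longer, the comparison is biased against TXA. Events are few: about 25 expected at the historic rate and about 13 at the target rate. One to four extra women therefore matter.

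**Working it through.** **Inputs from the protocol.** Historic rate p0 = 2.86%; a 50% reduction, so p1 = 1.43%; n = 890; one arm. Significance level, sidedness and power are not stated.

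**Reproducing 890.** For one sample against a fixed rate,

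n = [(z_a √(p0(1−p0)) + z_b √(p1(1−p1))) / (p0−p1)]².

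With two-sided 0.05 and 80% power: [(1.960 × 0.16668 + 0.8416 × 0.11872) / 0.0143]² = [0.42661 / 0.0143]² = 890.0. One-sided 0.05 with 90% power gives 889, so the level is inferred rather than known. The two-sample formula gives 1,611 per group and does not reproduce the figure.

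**Baseline.** Expected events are 890 × 0.0286 = 25.5 and 890 × 0.0143 = 12.7. In an exact binomial test at one-sided 0.025, P(X ≤ 15 | 2.86%) = 0.017 and P(X ≤ 16 | 2.86%) = 0.030, so the cutoff is 15 or fewer. Power is P(X ≤ 15 | 1.43%) = 0.789. The normal approximation gives 0.800. The plan names a chi-square test; the exact test is used here as a check.

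**Extra events.** Let u be the proportion of women with a late or unrelated transfusion and under 1000 cc lost. Women who lost more are events anyway. The documents give no value for u, so 0.1% to 0.5% is assumed.

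- Study only, not affected by TXA: rates p0 and p1 + u. Exact power is P(X ≤ 15 | p1 + u).
- Added to both periods, not affected by TXA: rates p0 + u and p1 + u.
- Added to both periods, halved by TXA: rates p0 + u and (p0 + u)/2.

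Normal-approximation power is Φ{[(difference in rates) × √890 − 1.960 √(p0*(1−p0*))] / √(p1*(1−p1*))}, where p0* and p1* are the two rates in each case.

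| u | Extra women (890u) | Study only, exact | Study only, normal | Both, unaffected, normal | Both, halved, normal |
|---|---|---|---|---|---|
| 0.1% | 0.9 | 71% | 72% | 78% | 82% |
| 0.2% | 1.8 | 62% | 62% | 76% | 83% |
| 0.3% | 2.7 | 53% | 53% | 74% | 85% |
| 0.5% | 4.5 | 35% | 36% | 70% | 88% |

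**Bias.** In the study-only case a true 50% reduction would appear as 1 − (1.43% + u)/2.86%, which is 46.5%, 43.0%, 39.5% and 32.5%.

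**A variant.** Suppose the quoted 2.86% already contains u and TXA halves only the rest. The study rate is then (p0 − u)/2 + u = p1 + u/2, and power is 76%, 72%, 67% and 58%. The same figures apply if the extra events are halved by TXA but counted only in the study.

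**Sensitivity to the assumed level.** At one-sided 0.05 the exact cutoff is 17 (P = 0.0485 at 2.86%). Baseline power P(X ≤ 17 | 1.43%) is 91%, and P(X ≤ 17 | p1 + u) is 86%, 79%, 72% and 55% in the study-only case.

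**The case against.** The strongest reply is that counting every transfusion was deliberate. The rule says that transfusion counts below 1000 cc, and the protocol names fewer transfusions, less symptomatic anemia and preserved blood stock as aims. A transfusion on day 2 for anemia caused by delivery bleeding is plausibly a target event, and a strict 24-hour limit would remove it. This stands, and it is why the window should be the sponsor's choice. It does not justify having no window.

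It can also be said that the 24 hours carries over from the cited definition, or that follow-up to six weeks does not mean hemorrhage is ascertained for six weeks. The second point is correct: the text does not say so, and the safety plan describes data collection around delivery. However, outpatient records are a listed source, so late capture is possible, and nothing in the visible text restores a limit. A figure beside the definitions and the data collection sheet are not visible and could bear on timing.

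A reader might infer that an antepartum transfusion for anemia would count, because follow-up starts at enrollment. The documents do not support that: the rule defines postpartum hemorrhage, and a prenatal transfusion is not postpartum.

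A reader might also infer that the definition necessarily lowers power. That does not follow either. It depends on an unstated rate, on whether the extra events respond to TXA, and on how the 2.86% was counted.

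**Conclusion.** The concern holds in conditional form. The primary rule lacks a window and a bleeding indication, and the benchmark lacks a stated definition, so the two rates may count different events. The direction is against TXA if the historic span was shorter; otherwise it is not determined by the documents.

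The larger power losses, and the reading of a true halving as a 32.5% to 46.5% reduction, need three assumptions together: u of 0.1% to 0.5%, no effect of TXA on those events, and a historic rate that omits them. When unaffected events add to both rates the loss is modest. When responsive events do so, there is no loss. The level of one-sided 0.025 is assumed throughout except in the stated sensitivity check. Unequal counting between the periods is the main risk; dilution by unaffected events is secondary.

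**What to change.** Define the primary outcome as blood loss of at least 1000 cc, or transfusion for peripartum bleeding, within one stated window after birth, including intrapartum loss. The window can be the cited 24 hours, or the delivery stay if the sponsor wants to keep later transfusions for delivery blood loss. Apply the identical definition, window and record sources to the historic cohort. Restate the 2.86% under that definition, and the basis for 890 with its significance level and power. Report later or unrelated transfusions under the existing secondary transfusion outcome.

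The wording is short. The real cost is classifying historic transfusions by time and indication at chart level. This adds to the review already planned, which covers transfusion as a secondary outcome but relies on record sampling. Late bleeds leave the primary outcome. No extra visits or tests are needed.
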